9.0 Ancillary Treatment/Supportive Care

- 9.1 Antiemetics may be used at the discretion of the attending physician.
- 9.2 Blood products and growth factors should be utilized as clinically warranted and following institutional policies and recommendations. The use of growth factors should follow published guidelines of the American Society of Clinical Oncology (42) Update of Recommendations for the Use of Hematopoietic Colony-Stimulating Factors: Evidence-Based, Clinical Practice Guidelines. *J Clin Oncol* July 1, 2006, vol. 24 no. 19 3187-3205.
- 9.3 Patients should receive full supportive care while on this study. This includes blood product support, antibiotic treatment, and treatment of other newly diagnosed or concurrent medical conditions. All blood products and concomitant medications such as antidiarrheals, analgesics, and/or antiemetics received from the first day of study treatment administration until 30 days after the final dose will be recorded in the medical records.
- 9.4 **Vascular Occlusion**

Arterial and venous thrombosis and occlusions, including fatal myocardial infarction, stroke, stenosis of large arterial vessels of the brain, severe peripheral vascular disease, and the need for urgent revascularization procedures have occurred in at least 27% of Iclusig-treated patients from the phase 1 and phase 2 trials. Iclusig can cause fatal and life-threatening vascular occlusion within 2 weeks of starting treatment. Iclusig can also cause recurrent or multi-site vascular occlusion.

The median time to onset of the first vascular occlusion event was 5 months. Iclusig can cause fatal and life threatening vascular occlusion in patients treated at dose levels as low as 15 mg per day.

Patients with and without cardiovascular risk factors, including patients age 50 years or younger, experienced these events. Vascular occlusion adverse events were more frequent with increasing age and in patients with prior history of ischemia, hypertension, diabetes, or hyperlipidemia (see Table 4).

Clinicians should consider whether the benefits of Iclusig treatment are expected to exceed the risks of therapy. In patients suspected of developing arterial thrombotic events, interrupt or stop Iclusig. A benefit-risk consideration should guide a decision to restart Iclusig therapy. Consider dose modification or discontinuation of Iclusig in patients who develop serious venous thromboembolism and **Monitor for evidence of thromboembolism and vascular occlusion. Interrupt or stop Iclusig immediately for vascular occlusion.**

9.5 **Hypertension**

Treatment-emergent hypertension occurred in 67% of patients (300/449). Eight (2%) treated with Iclusig in clinical trials experienced treatment-emergent symptomatic hypertension as a serious adverse reaction, including hypertensive crisis. Patients may require urgent clinical intervention for hypertension associated with confusion, headache, chest pain, or shortness of breath [*see Adverse Reactions (6)*]. In patients with baseline systolic BP < 140 mm Hg and baseline diastolic BP < 90 mm Hg, 78% (220/282) experienced treatment-emergent hypertension; 49% (139/282) developed Stage 1 hypertension (defined as systolic BP ≥ 140 mm Hg or diastolic BP ≥ 90 mm Hg) while 29% developed Stage 2 hypertension (defined as systolic BP ≥ 160 mm Hg or diastolic BP ≥ 100 mm Hg). In 131 patients with Stage 1 hypertension at baseline, 61% (80/131) developed Stage 2 hypertension. Monitor and manage blood pressure elevations during Iclusig use and treat hypertension to normalize blood pressure. Interrupt, dose reduce, or stop Iclusig if hypertension is not medically controlled.

9.6 **Heart Failure**

Fatal and serious heart failure or left ventricular dysfunction occurred in 5% of Iclusig-treated patients (N = 22). Eight percent of patients (N = 35) experienced any grade of heart failure or left ventricular dysfunction. Monitor patients for signs or symptoms consistent with heart failure and treat as clinically indicated, including interruption of Iclusig. Consider discontinuation of Iclusig in patients who develop serious heart failure

- 9.7 **Diarrhea:** This could be managed conservatively with loperamide. The recommended dose of loperamide is 4 mg at first onset, followed by 2 mg every 2-4 hours until diarrhea free (maximum 16 mg/day).

In the event of Grade 3 or 4 diarrhea, the following supportive measures are allowed: hydration, octreotide, and antidiarrheals.

If diarrhea is severe (requiring intravenous rehydration) and/or associated with fever or severe neutropenia (grade 3 or 4), broad-spectrum antibiotics must be prescribed. Patients with severe diarrhea or any diarrhea associated with severe nausea or vomiting **should be hospitalized** for intravenous hydration and correction of electrolyte imbalances.

- 9.8 **TLS:** Clinically significant Tumor Lysis Syndrome (TLS) has been reported at the initiation of treatment with TKIs in CML patients. The patients at risk of TLS are those with high tumor/leukemic burden prior to treatment. These patients should be monitored closely, especially at the initiation of treatment. Appropriate TLS precautions and prophylactic treatment (such as aggressive hydration with fluids and the initiation of allopurinol 600 mg/day or other appropriate treatments) should be initiated prior to the start of therapy for those at risk for TLS. Rasburicase and other appropriate treatments for hyperuricemia or TLS are permitted.

- 9.9a **Prolonged QTcF:** If a prolongation of QTcF is observed, it is important to perform serum electrolyte analysis (including potassium, calcium, and magnesium) and correct any significant abnormalities with supplements if below normal limits. It is also necessary to review all concomitant medications the patient is on and discontinue medications that are known or suspected to cause QT prolongation.

If no contributing reason is identified and the reason for QTcF prolongation is believed to be due to study medication, dose interruption and reduction guidelines for general non-hematologic toxicities in 8.2 for ponatinib should be followed. Additionally, weekly ECG monitoring is recommended for 4 weeks upon resumption of study drug, then monthly for 6 months, and then every 3 months for the remainder of the study, or more frequently as clinically indicated.

- 9.9b Based on *in vitro* studies, ponatinib is a substrate of CYP3A4/5 and to a lesser extent CYP2C8 and CYP2D6. Ponatinib also inhibits the P-glycoprotein (P-gp), ATP-binding cassette G2 (ABCG2) [also known as BCRP], and bile salt export pump (BSEP) transporter systems *in vitro*.

Drugs That Are Strong Inhibitors of CYP3A Enzymes

In a drug interaction study in healthy volunteers, co-administration of Iclusig with ketoconazole increased plasma ponatinib AUC_{0-inf} and C_{max} by 78% and 47%, respectively. When administering Iclusig with strong CYP3A inhibitors (e.g., boceprevir, clarithromycin, conivaptan, grapefruit juice, indinavir, itraconazole, ketoconazole, lopinavir/ritonavir, nefazodone, nelfinavir, posaconazole, ritonavir, saquinavir, telaprevir, telithromycin, voriconazole), the recommended starting dose should be reduced at the discretion of the treating physician. Patients taking concomitant strong inhibitors may be at increased risk for adverse reactions.

Drugs That Are Strong Inducers of CYP3A Enzymes

Coadministration of Iclusig with strong CYP3A inducers was not evaluated *in vitro* or in a clinical trial; however, a reduction in ponatinib exposure is likely. Coadministration of strong CYP3A inducers (e.g., carbamazepine, phenytoin, rifampin, and St. John's Wort) with Iclusig should be avoided unless the benefit outweighs the possible risk of ponatinib underexposure. Monitor patients for signs of reduced efficacy.

Drugs That Elevate Gastric pH

Coadministration of Iclusig with drugs that elevate the gastric pH was not evaluated in a clinical trial. Based on the chemical properties of ponatinib, elevated gastric pH may reduce bioavailability and exposure. Coadministration of Iclusig with drugs that elevate the gastric pH (e.g., proton pump inhibitors, H2 blockers, or antacids) should be avoided unless the benefit outweighs the possible risk of ponatinib underexposure. Monitor patients for signs of reduced efficacy.

Drugs That Are Substrates of the P-gp or ABCG2 Transporter Systems

In vitro studies demonstrate that Iclusig inhibits the P-gp and ABCG2 [also known as BCRP] transporter systems. The effect of coadministration of Iclusig with sensitive substrates of the P-gp (e.g., aliskiren, ambrisentan, colchicine, dabigatran etexilate, digoxin, everolimus, fexofenadine, imatinib, lapatinib, maraviroc, nilotinib, posaconazole, ranolazine, saxagliptin, sirolimus, sitagliptin, tolvaptan, toptecan) and ABCG2 [also known as BCRP] (e.g., methotrexate, mitoxantrone, imatinib, irinotecan, lapatinib, rosuvastatin, sulfasalazine, toptecan) transporter systems on exposure of these substrates has not been evaluated in clinical studies.

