	Alanine aminotransferase increased (ALT) OR Aspartate aminotransferase increased (AST) ≥ Grade 3 AND Blood bilirubin increased ≥ 2 x ULN AND Alkaline phosphatase > 2 x ULN	Ponatinib	Discontinue ponatinib
Gastrointestinal Disorders	Pancreatitis ≥ Grade 2	Ponatinib	Omit ponatinib Perform ultrasound or abdominal CT scan with contrast If imaging is positive, continue to omit ponatinib and repeat according to clinical care If imaging is negative, or after resolution by imaging, resume at 45 mg after recovery to ≤ grade 1 Recurrence at 45 mg: Repeat above, except resume at 30 mg after recovery to ≤ grade 1 Recurrence at 30 mg: Repeat above, except resume at 15 mg after recovery to ≤ grade 1 Recurrence at 15 mg: Discontinue ponatinib

→ → Use the NCI Common Terminology Criteria for Adverse Events (CTCAE) version 4.0* unless otherwise specified ← ←			
CTCAE System/Organ/Class (SOC)	ADVERSE EVENT	AGENT	ACTION**
	Pancreatitis ≥ Grade 3	Ponatinib	Omit ponatinib Perform ultrasound or abdominal CT scan with contrast If imaging is positive, continue to omit ponatinib and repeat according to clinical care If imaging is negative, or after resolution by imaging, resume at 30 mg after recovery to ≤ grade 1 Recurrence at 30 mg: Repeat above, except resume at 15 mg after recovery to ≤ grade 1 Recurrence at 15 mg: Discontinue ponatinib
	Pancreatitis ≥ Grade 4	Ponatinib	Discontinue ponatinib
Nervous System Disorders	Stroke any Grade	Ponatinib	Discontinue ponatinib
	Peripheral sensory neuropathy ≥ Grade 2	Ponatinib	Please see section 8.43 below for guidance
Cardiac Disorders	Left ventricular systolic dysfunction ≥ Grade 3	Ponatinib	Omit ponatinib Resume at 45 mg after recovery to ≤ grade 1 Recurrence at 45 mg : Omit ponatinib Resume at 30 mg after recovery to ≤ grade 1 Recurrence at 30 mg: Omit ponatinib Resume at 15 mg after recovery to ≤ grade 1 Recurrence at 15 mg: Discontinue ponatinib
	Left ventricular systolic dysfunction ≥ Grade 4		Discontinue ponatinib
	Myocardial Infarction any Grade		Discontinue ponatinib

→ → Use the NCI Common Terminology Criteria for Adverse Events (CTCAE) version 4.0* unless otherwise specified ← ←

CTCAE System/Organ/Class (SOC)	ADVERSE EVENT	AGENT	ACTION**

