Skin and subcutaneous tissue disorders	Rash maculo-papular ≥ Grade 2 despite optimal symptomatic therapy	Ponatinib	Omit ponatinib Resume at 45 mg after recovery to ≤ grade 1 Recurrence at 45 mg: Omit ponatinib Resume at 30 mg after recovery to ≤ grade 1 Recurrence at 30 mg: Omit ponatinib Resume at 15 mg after recovery to ≤ grade 1 Recurrence at 15 mg: Discontinue ponatinib
	Rash maculo-papular ≥ Grade 3 despite optimal symptomatic therapy		Omit ponatinib Resume at 30 mg after recovery to ≤ grade 1 Recurrence at 30 mg: Omit ponatinib Resume at 15 mg after recovery to ≤ grade 1 Recurrence at 15 mg: Discontinue ponatinib
Vascular Disorders			
	Thromboembolic event ≥ Grade 1		Discontinue ponatinib

→ → Use the NCI Common Terminology Criteria for Adverse Events (CTCAE) version 4.0* unless otherwise specified ← ←			
CTCAE System/Organ/Class (SOC)	ADVERSE EVENT	AGENT	ACTION**
	Hypertension Grade 2 or 3		
Antihypertensive medication should be initiated or optimized to achieve target blood pressure before interruption or dose reduction of the study treatment at the discretion of the investigator. If hypertension is persistent despite adequate anti-HTN therapy including titration of anti-HTN medication or introduction of additional anti-HTN medications, dose interruption and reduction is recommended according to the below guidelines:
 
Hold ponatinib Resume at 30 mg after recovery to ≤ grade 1
 
Recurrence at 30 mg Omit ponatinib Resume at 15 mg after recovery to ≤ grade 1
 
Recurrence at 15 mg Discontinue ponatinib

	Hypertension ≥ Grade 4	Ponatinib	
Omit ponatinib Resume at 30 mg after recovery to ≤ grade 1
 
Recurrence at 30 mg Omit ponatinib Resume at 15 mg after recovery to ≤ grade 1
 
Recurrence at 15 mg Discontinue ponatinib

Injury, poisoning and procedural complications	Wound complication ≥ Grade 2	Ponatinib	See section 8.47 for guidance
General disorders and administrative site conditions	Edema limbs ≥ Grade 2	Ponatinib	See section 8.45 for guidance
Eye Disorders	Eye Disorders – Other	Ponatinib	See section 8.44 for guidance

→ → Use the NCI Common Terminology Criteria for Adverse Events (CTCAE) version 4.0* unless otherwise specified ← ←

CTCAE System/Organ/Class (SOC)	ADVERSE EVENT	AGENT	ACTION**

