Other Non-Hematologic events	≥ Grade 3	Ponatinib	Omit drug and follow patient at least weekly until adverse event has resolved to grade ≤ 2, restart agent at next lower dose level. See sections 8.41 through 8.47 for guidance on other non-hematologic events

* Located at http://ctep.cancer.gov/protocolDevelopment/electronic_applications.ctc.htm

** Use the following to describe actions in the Action column:

- Omit = Treatment is not given for the day/days that are omitted and will not be made up, but treatment may resume once the adverse event has resolved as mandated in Table 8.2. For example, if treatment is omitted on Day 8, but the adverse event has resolved by Day 15, treatment may resume on Day 15.
- Hold/Delay = Treatment can be made up as part of this cycle
- Discontinue = Treatment is totally stopped

NOTE: If the patient experiences a significant adverse event requiring a dose reduction at the start of the next cycle, then the dose will remain lowered for that entire subsequent cycle. If that cycle is completed with no further adverse events >Grade 2, then the dose may be increased, at the investigator's discretion, one level at a time, in the following cycles.

NOTE: Adverse events requiring a dose-reduction step for any or all drugs beyond the two dose-reduction steps (levels -1 and -2) will be at the discretion of the treating physician, if the decision is made for the patient to be kept on study. These dose reductions must be clearly recorded in reported clinical data.

- 8.3 A new course of treatment may begin on the scheduled Day 1 of a new cycle if:
- The ANC is $\geq 1500/\mu\text{L}$;
 - The platelet count is $\geq 75,000/\mu\text{L}$;
 - Any other Ponatinib related adverse event that may have occurred has resolved to \leq Grade 1 or baseline severity.

If these conditions are not met on scheduled Day 1 of a new cycle, the subject will be evaluated at least weekly and the new cycle of treatment will not be initiated until the adverse event has resolved as described above.

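### Section 9.4 leaves room to continue or restart ponatinib after vascular events for which Table 8.2 requires a total stop; separately, one lipase draw asked for in Section 8.42 is not scheduled

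*Combined protocol and SAP*

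**What the plan says.** **Table 8.2.** The triggers "Thromboembolic event ≥ Grade 1", "Stroke any Grade" and "Myocardial Infarction any Grade" all carry the same action, to discontinue ponatinib. The notes under the table say "Discontinue = Treatment is totally stopped", which separates this action from omitting or holding doses. None of the three rows has a resume step.

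**Section 9.4.** For venous events it says "Consider dose modification or discontinuation of Iclusig in patients who develop serious venous thromboembolism". For vascular occlusion generally it says "Interrupt or stop Iclusig immediately for vascular occlusion". For suspected arterial thrombotic events it allows interruption or stopping and lets benefit-risk guide a restart. It also warns that "Iclusig can cause fatal and life threatening vascular occlusion in patients treated at dose levels as low as 15 mg per day".

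**Lipase.** Section 8.42 asks for a check every two weeks during the first two months and monthly after that, or as clinically indicated. The Section 4.0 schedule has lipase at screening, on Cycle 1 Days 1, 8, 15 and 22, and then on Day 1 of each later cycle.

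**The concern.** A serious venous thromboembolism falls within the Grade 1 or higher row of Table 8.2, so the table requires the drug to stop. A clinician reading Section 9.4 for the same patient is offered a reduced dose as an alternative. Likewise, a confirmed stroke or myocardial infarction must end treatment under the table, while the benefit-risk restart in Section 9.4 is not limited to events that have been ruled out.

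What is at stake is patient safety and adherence to the protocol. The situation can arise: exclusion 3.29h bars active venous thromboembolism only when it cannot be treated with anticoagulants, so some patients with a treated clot may enrol. The lowest dose level defined in Section 8.1 is 15 mg, which is also a dose at which Section 9.4 reports fatal occlusion. Section 10.41 requires vascular occlusive events to reach the manufacturer within 2 business days. That would reveal inconsistent handling afterwards but does not set the dose.

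The lipase point is separate and smaller. Section 8.42 reports treatment-emergent lipase elevation in 41% of earlier patients, and one of the two-weekly checks it asks for has no place in the schedule.

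**Working it through.** The plan gives no figure to reproduce for the dosing point, so the check is a comparison of the two texts by clinical situation.

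1. *Suspected event, not yet confirmed.* Section 9.4: interrupt or stop. Table 8.2 has no row for a suspicion. The two are compatible, since interrupting is a sensible first step.
2. *Confirmed serious venous thromboembolism.* Table 8.2: total stop. Section 9.4: modify the dose or discontinue. They conflict if the dose is modified.
3. *Confirmed stroke or myocardial infarction.* Table 8.2: total stop. Section 9.4: interrupt or stop, with a restart possible on benefit-risk grounds. They conflict if the drug is restarted.
4. *Other confirmed occlusive events listed in Section 10.41, such as transient ischemic attack, angina or peripheral arterial occlusive disease.* Table 8.2 does not name these. Section 9.4 supplies the action, so its wording is still needed here.

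Next, is there a clause that decides between the texts?

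- The rule in Section 8.0 about taking the greatest reduction covers several adverse events in one patient, not two instructions for one event.
- The last row of Table 8.2 refers to Sections 8.41 to 8.47, not to 9.4.
- Section 9.9a sends drug-related QTcF prolongation back to Section 8.2. Section 9.4 has no such link.

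Would a general rule that the table governs be safe? Two comparisons say no.

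- *Pancreatitis.* For events that allow a restart, the table permits it after recovery to Grade 1 or lower with negative or resolved imaging. Where lipase rises with abdominal symptoms, Section 8.42 also requires complete symptom resolution and lipase below 1.5 x ULN.
- *Tachyarrhythmia.* Section 8.46 calls for interruption and evaluation with no grade threshold. The table's general non-hematologic row starts at Grade 3.

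In both, letting the table win would loosen the safeguard.

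**Lipase arithmetic**, with 28-day cycles starting on time:

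- Days wanted by Section 8.42: 1 + 14k for k = 0 to 4, giving days 1, 15, 29, 43 and 57 (5 points).
- Days scheduled in Section 4.0 from Day 1: 1, 8, 15, 22, then 1 + 28 = 29 and 1 + 56 = 57 (6 draws).
- Wanted but not scheduled: day 43, which is Cycle 2 Day 15 (1 of 5).
- Gap: 57 − 29 = 28 days, against 14 wanted.
- With the ±2-day windows: shortest 55 − 31 = 24 days, longest 59 − 27 = 32 days.

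**The case against.** The strongest reply is that the structure already settles the matter. Section 8 is the dose-modification section and Section 9 covers supportive care. The table's notes treat it as binding ("treatment may resume once the adverse event has resolved as mandated in Table 8.2"). Rows that defer to narrative text say so, and the thromboembolic row does not. Section 9.4 only asks the clinician to consider options, and one of them is discontinuation, so a clinician who stops the drug satisfies both texts. Section 9.4 also reads like general product information. Most of this stands, and it is why the point is minor. What remains is that Section 9.4 is worded as an instruction, gives a second option that the table does not allow, and does not point back to the table.

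The venous sentence also breaks off in the text available, possibly through PDF reading. The argument uses only the words present, but the full sentence should be checked before amending. The sentence on interrupting or stopping is complete.

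On lipase, the reply is that Section 4.0 gives 6 draws by day 57 where Section 8.42 needs 5, with weekly sampling in Cycle 1. Section 8.42 also requires interruption and evaluation when lipase rises with abdominal symptoms. Both are fair. The total is adequate; only the spacing in the second month falls short.

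A reader might go further and infer that patients will be kept on drug after a clot in meaningful numbers, using the 27% in Section 9.4. The documents do not support that. The figure is a floor for arterial and venous events combined in earlier trials, and no venous rate is given. Nor does the 15 mg warning measure the risk of continuing after a venous event: it covers all vascular occlusion, and 15 mg is simply the lowest defined level, with steps beyond it left to the physician.

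**Conclusion.** The inconsistency is real and minor. For confirmed serious venous thromboembolism, Section 9.4 permits dose modification where Table 8.2 requires a total stop. For confirmed stroke or myocardial infarction, its restart wording is looser than the table. It causes harm only if a clinician follows the looser option in Section 9.4, and no frequency can be put on that from the documents.

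A reader might infer that Section 9.4 overrides the table, or that the two-stage decision is distorted. Neither follows. The layout favours the table. The documents also give nothing from which to derive the direction or size of any effect on clinical benefit, so none is claimed.

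The lipase gap is one missing two-weekly check (day 43), leaving 28 days unsampled, or 24 to 32 with visit windows. This assumes that cycles start on schedule; a delayed Cycle 3 under Section 8.3 would lengthen it. The documents do not say how many elevations begin in that interval.

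**What to change.** **Section 9.4.** Amend it to state three things:

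- for a suspected event, interrupt ponatinib and evaluate, and restart only if the event is ruled out;
- for a confirmed thromboembolic event of Grade 1 or higher, or a stroke or myocardial infarction of any grade, discontinue as in Table 8.2;
- for the other confirmed vascular occlusive events listed in Section 10.41, keep the present instruction to interrupt or stop immediately.

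**Precedence.** Do not add a blanket statement that Table 8.2 governs. If a line is wanted, say that the more restrictive instruction applies, so that the stricter rules in Sections 8.42 and 8.46 stand.

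**Section 4.0.** Add a lipase draw at Cycle 2 Day 15.

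**Cost.** The dosing change is a few sentences of amendment text. A patient who is benefiting and has a low-grade clot loses the drug, but Table 8.2 already requires that. Lipase tests are already research funded (Section 19.2). However, Section 4.0 has no Cycle 2 Day 15 visit and Section 7.2 requires a return only at least every 28 days, so the draw may need an extra laboratory visit.

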- 3.29h Clinically significant, uncontrolled, or active cardiovascular disease, specifically including, but not restricted to:
 - Any history of myocardial infarction, stroke, or revascularization
 - Unstable angina or transient ischemic attack within 6 months prior to registration

- Congestive heart failure within 6 months prior to registration, or left ventricular ejection fraction (LVEF) less than lower limit of normal per local institutional standards within 6 months prior to registration
 - History of clinically significant (as determined by the treating physician) atrial arrhythmia
 - Any history of ventricular arrhythmia
 - Active venous thromboembolism including deep venous thrombosis or pulmonary embolism that is not amenable to treatment with anticoagulants.
 - Patients with congenital prolonged QT syndromes and abnormal baseline prolonged QTc (>450 ms in men and >470 ms in women).
 - Patients with an ejection fraction $\leq 50\%$ as assessed by a baseline echocardiogram.
- 3.29i Taking medications that are known to be associated with Torsades de Pointes (see Appendix XII)
- 3.29j Taking any medications or herbal supplements that are known to be strong inhibitors of CYP3A4 ≤ 14 days prior to registration. (see Section 9.9b)

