Appendix XII: Prohibited Drugs Affecting the QT Interval

The list of drugs that can be associated with Torsades de Pointes or prolonged QT interval is shown on the table below. This can also be found online at <http://www.azcert.org/medical-pros/drug-lists/bycategory.cfm>.

Three categories of drugs are listed on this website. Concomitant use of drugs in the first category (Drugs with Risk of Torsades de Pointes) is prohibited, and these drugs are listed below. Agents in the 2 categories of lesser risk (Drugs with Possible Risk of Torsades de Pointes; and Drugs with Conditional Risk of Torsades de Pointes) should be avoided. Note: these are available on the website, but are not listed in the table below.

Table B-1 Drugs Generally Accepted by the QTDrugs.org Advisory Board of the Arizona CERT to have a Risk of Causing Torsades de Pointes and Prohibited in this Study

Generic Name	Brand Name	Class/Clinical Use
Amiodarone	Cordarone®	Anti-arrhythmic / abnormal heart rhythm
Amiodarone	Pacerone®	Anti-arrhythmic / abnormal heart rhythm
Arsenic trioxide	Trisenox®	Anti-cancer / Leukemia
Astemizole	Hismanal®	Antihistamine / Allergic rhinitis
Bepidil	Vascor®	Anti-anginal / heart pain
Chloroquine	Aralen®	Anti-malarial / malaria infection
Chlorpromazine	Thorazine®	Anti-psychotic/ Anti-emetic / schizophrenia/ nausea
Cisapride	Propulsid®	GI stimulant / heartburn
Clarithromycin	Biaxin®	Antibiotic / bacterial infection
Disopyramide	Norpace®	Anti-arrhythmic / abnormal heart rhythm
Dofetilide	Tikosyn®	Anti-arrhythmic / abnormal heart rhythm
Domperidone	Motilium®	Anti-nausea / nausea
Droperidol	Inapsine®	Sedative; Anti-nausea / anesthesia adjunct, nausea
Erythromycin	Erythrocin®	Antibiotic; GI stimulant / bacterial infection; increase GI motility
Erythromycin	E.E.S.®	Antibiotic; GI stimulant / bacterial infection; increase GI motility
Halofantrine	Halfan®	Anti-malarial / malaria infection
Generic Name	Brand Name	Class/Clinical Use

Haloperidol	Haldol®	Anti-psychotic / schizophrenia, agitation
Ibutilide	Corvert®	Anti-arrhythmic / abnormal heart rhythm
Levomethadyl	Orlaam®	Opiate agonist / pain control, narcotic dependence
Mesoridazine	Serentil®	Anti-psychotic / schizophrenia
Methadone	Dolophine®	Opiate agonist / pain control, narcotic dependence
Methadone	Methadose®	Opiate agonist / pain control, narcotic dependence
Pentamidine	Pentam®	Anti-infective / pneumocystis pneumonia

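### Section 9.9b handles clarithromycin by reducing the ponatinib dose while Appendix XII prohibits it, and its dose wording does not fit an inhibitor begun during treatment

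*Combined protocol and SAP*

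**What the plan says.** Section 9.9b, under strong CYP3A inhibitors, begins "When administering Iclusig with strong CYP3A inhibitors (e.g., boceprevir, clarithromycin, conivaptan" and continues with 13 further examples. The instruction is that "the recommended starting dose should be reduced at the discretion of the treating physician". It adds: "Patients taking concomitant strong inhibitors may be at increased risk for adverse reactions". For strong inducers the same section is firmer, stating that co-administration "with Iclusig should be avoided unless the benefit outweighs the possible risk of ponatinib underexposure". It takes a similar line on drugs that raise gastric pH, but not on inhibitors.

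Appendix XII says: "Concomitant use of drugs in the first category (Drugs with Risk of Torsades de Pointes) is prohibited". The title of Table B-1 describes its drugs as accepted "to have a Risk of Causing Torsades de Pointes and Prohibited in this Study", and clarithromycin has a row in that table.

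Both groups are barred at entry. Exclusion 3.29i covers patients "Taking medications that are known to be associated with Torsades de Pointes (see Appendix XII"). Exclusion 3.29j covers strong CYP3A4 inhibitors taken within 14 days "prior to registration. (see Section 9.9b"), so it relies on the 9.9b list.

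Section 8.1 identifies the starting dose as level 0, 45 mg once daily, with 30 mg and 15 mg below it. Section 15.16 advises that strong CYP3A4 inhibitors be used cautiously or not at all.

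**The concern.** Starting an antibiotic during treatment is foreseeable, since Section 9.3 includes antibiotics in supportive care. A physician considering clarithromycin who consults the interaction text in Section 9 finds it named, with a dose reduction as the response. Nothing there points to Appendix XII, which is cited only in the contents list and in exclusion 3.29i. The physician could therefore give a drug that the study prohibits for QT risk alongside one for which Section 15.17 itself lists QT prolongation as an infrequent effect.

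The second issue concerns the other inhibitors. An instruction about the starting dose does not plainly tell the physician what to do for a patient already on 45, 30 or 15 mg. Higher exposure matters with this drug: Section 9.4 warns of fatal vascular occlusion at doses as low as 15 mg per day.

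**Working it through.** **Step 1: overlap of the two lists.** Section 9.9b names 16 inhibitors. Table B-1 has 34 rows. Six generics (amiodarone, erythromycin, methadone, pentamidine, procainamide, quinidine) appear under two brand names each, so there are 34 − 6 = 28 distinct generics. The two lists share one drug, clarithromycin. Appendix XII does not list the two lesser-risk QT categories, so they were not checked.

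**Step 2: the rules for clarithromycin.**

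| Place | Rule |
|---|---|
| 3.29i with Appendix XII | Excluded at entry |
| 3.29j with 9.9b | Excluded if taken within 14 days before registration |
| Appendix XII, Table B-1 | Prohibited during the study |
| 9.9b | Reduce the starting dose, amount left to the physician |
| 15.16 | Caution or avoidance, as for any strong CYP3A4 inhibitor |

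The entry rules agree with each other. The on-study rules in 9.9b and Appendix XII do not, and neither cites the other.

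**Step 3: when a starting-dose rule could apply.** Under 3.29j a patient has taken no strong inhibitor in the 14 days before registration. Under 6.6 treatment begins within 7 days after registration. A strong inhibitor can therefore be present at the first dose only if it was begun in a gap of at most 7 days. Any later use falls during treatment, where a single cycle already lasts 28 days, or 28 / 7 = 4 times that gap.

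**Step 4: why the dose level matters.** Section 9.9b reports that ketoconazole raised ponatinib AUC by 78% and Cmax by 47% in healthy volunteers. Assume the same ratios in patients, and the approximate dose proportionality that Section 15.15 describes for 15 to 60 mg. The equivalent dose without inhibitor is then dose × 1.78 by AUC and dose × 1.47 by Cmax.

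- 30 mg with inhibitor: 30 × 1.78 = 53.4 mg by AUC, and 53.4 / 45 = 119% of the 45 mg exposure. By Cmax, 30 × 1.47 = 44.1 mg, and 44.1 / 45 = 98%.
- 15 mg with inhibitor: 15 × 1.78 = 26.7 mg by AUC, and 26.7 / 45 = 59%. By Cmax, 15 × 1.47 = 22.05 mg, and 22.05 / 45 = 49%.
- 45 mg left unchanged: 45 × 1.78 = 80.1 mg by AUC. This lies beyond 60 mg and is illustrative only.

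From 45 mg, neither lower level restores the original AUC under these assumptions. One step leaves it about 19% high and two steps about 41% low.

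**The case against.** Section 9.9b is conditional. It says what to do when a strong inhibitor is given and does not expressly permit any of them. Its list is illustrative, while Appendix XII is a specific ban, so a careful reader can obey both by applying the stricter rule. On the dose wording, the opening words can be read to cover an inhibitor begun at any time, 8.1 supplies lower levels, and 15.16 already advises caution. Safeguards exist: both groups are barred at entry, patients are seen at least every 28 days (7.2), concomitant medication is recorded at each evaluation (18.1), and 9.9a has QT-prolonging drugs stopped if QTcF lengthens.

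Much of this stands, and it limits the point. A reader might infer that the protocol allows clarithromycin at a lower ponatinib dose, or that it gives no usable guidance for inhibitors begun during treatment. The documents support neither reading. What remains is that no section ranks 9.9b against Appendix XII, that the text most likely to be consulted omits the ban, and that the advice to avoid inhibitors sits in a different section from the dose instruction.

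A reader might also infer that a fixed one-level reduction is needed. The text does not support that: leaving such choices to the physician is consistent with the rest of the protocol, and Step 4 shows that a compulsory step from 45 to 30 mg would leave AUC at 119% while removing the option of 15 mg. Nor do the restart rules in 8.3 need an exemption. Section 8.0 concerns adverse events, the notes to Table 8.2 define omission by resolution of an adverse event, and reductions beyond level −2 are already left to the physician.

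**Conclusion.** The point holds as an internal inconsistency confined to one drug, together with dose wording that misfits its main use. It is worth correcting because the possible consequence is co-administration of a drug banned for QT risk and the correction costs almost nothing. The finding on the lists and the 7-day gap rests on the text alone. Only the exposure figures carry assumptions: that the ketoconazole ratios apply to patients and to the inhibitor used, and that exposure is proportional to dose. They show that the choice of level matters, not which level is right. The documents do not say how many patients would take a strong inhibitor, so the number affected cannot be estimated. A reader might infer some effect on the trial's error rates or sample size. There is none: the two-stage design in Section 16.2 does not depend on these rules.

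**What to change.** 1. Keep clarithromycin in the 9.9b list, because 3.29j relies on that list for its 14-day exclusion, but annotate it there as prohibited in this study, with a reference to Appendix XII.
2. Replace the dose sentence in 9.9b with wording such as: *Avoid strong CYP3A inhibitors during study treatment unless the benefit justifies the higher ponatinib exposure. If one that is not in Appendix XII is required, reduce the current ponatinib dose to a lower Section 8.1 level, chosen by the treating physician, while it is taken.*
3. Add a cross-reference from 15.16 to 9.9b.

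Section 8.1 has no level below 15 mg, so a patient already at that dose would remain a matter for the physician's judgment.

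The cost is a short text amendment and a slightly narrower choice of concomitant drugs. No visits, procedures, analyses or sample-size figures change.
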